## 7.2 DURATION OF STUDY PARTICIPATION FOR EACH PARTICIPANT

There will be no prospective follow-up period.

Property of the Sanofi-Aventis Groupe - strictly confidential

Protocol template for disease observational studies					
				Research and Development	
QSD-003149	Disease observational study	with disease	Application Date (DD/MM/YYYY) : dd-Mmm-09/11/2020	EFFECTIVE	

<DD-MM-YYYY HH:mm:ss> < 15-01-2021 21:03:21 > UTC

Formatted: Left, Tab stops: 8,89 cm, Centered + 17,1 cm, Right

primary data collection  
Study Number: GER-CAD-19-11180

Version number: ~~V6~~V7.0

## 8 SELECTION OF PARTICIPANTS

### 8.1 NUMBER OF PARTICIPANTS

It is planned to globally recruit approximately 170 participants in up to 12 centers in the 3 countries of interest (Germany, Italy and Austria).

At each site, all CAD patients diagnosed between January 1st, 2009 and January 1st, 2019 will be screened to confirm their eligibility against all study inclusion and exclusion criteria (a screening form will be provided online to support patient screening).

### 8.2 INCLUSION CRITERIA

Patients must meet all the following criteria to be eligible for the study:

- Patient aged  $\geq 18$  years
- Patient who fully meet the diagnostic criteria per section 7.1:
- Evidence of a signed and dated informed consent document indicating that the patient (or a legally acceptable representative) has been informed of all pertinent aspects of the study. A request for a waiver of informed consent for patients deceased, lost to follow up or alive but did not visit the site at time of data collection will be requested, where applicable.

### 8.3 EXCLUSION CRITERIA

Patients who exhibit any of the following must be excluded from the study:

- Patient with any form of hemolytic anemia other than CAD, including CAS and mixed AIHA
- Presence of records of any cause of secondary CAS at diagnosis [concurrent diagnosis of any type of lymphoma, multiple myeloma, chronic lymphocytic leukemia, Waldenström macroglobulinemia, other active cancer, or recent infection with mycoplasma pneumoniae Epstein-Barr virus, cytomegalovirus, autoimmune disorders (SLE)]

Protocol template for disease observational studies				
			Research and Development	
QSD-003149	Disease observational study	with disease	Application Date (DD/MM/YYYY) :dd-Mmm-09/11/2020	EFFECTIVE

<DD-MM-YYYY HH:mm:ss> < 15-01-2021 21:03:21 > UTC

primary data collection  
Study Number: GER-CAD-19-11180

Version number: ~~V6~~V7.0

#### 8.4 MODALITIES OF RECRUITMENT

Primary medical records will be available for review from specialty clinics treating CAD patients who agreed to participate in the patient chart review following a feasibility study.

Using the online screening form, study investigators routinely involved in the management of CAD patients (or delegates at the study site) will screen medical records of their patients diagnosed with CAD between January 1st, 2009 and January 1st, 2019 in a consecutive, retrospective order and include all those who fulfil pre-defined study eligibility criteria. Patient selection will be based on systematic sampling, *i.e.* all consecutive eligible patients are expected to be included in the study. Target sample size will be approximately 170 charts.

Property of the Sanofi-Aventis Groupe - strictly confidential

Protocol template for disease observational studies				
			Research and Development	
QSD-003149	Disease observational study protocol v. 6.0	with disease	Application Date (DD/MM/YYYY) :dd-Mmm- 09/11/2020	EFFECTIVE

<DD-MM-YYYY HH:mm:ss> <15-01-2021 21:03:21 > UTC

Formatted: Left, Tab stops: 8,89 cm, Centered + 17,1 cm, Right

primary data collection  
Study Number: GER-CAD-19-11180

Version number: ~~V6~~V7.0

## 9 SELECTION OF INVESTIGATORS

A list of sites managing CAD patients in each participating country will be designed by Cerner Enviza and the Sponsor based on data availability and characteristics of the health care system of each study country. In Germany, a comprehensive list of hematology and oncology hospitals potentially managing CAD patients across the country will be created from several sources, including Orphanet and PubMed. In Italy and Austria, a list of referral centers managing CAD patients based on existing input from pre-marketing clinical studies, local affiliates of the Sponsor and external advisors will be used for site selection.

A feasibility study will be run to select study sites from such lists. A site qualification questionnaire tailored to the study and country will be designed to evaluate feasibility and verification of the capability and willingness of the potential sites to complete the study. During the feasibility stage, research assistants will contact physicians from each site for completion of the site qualification questionnaire over the phone or via email to determine both site and physician eligibility to participate in the study. If a physician does not qualify for the study or refuses to participate in the study, he/she may refer another physician in the same hospital. If he/she qualifies but refuses to participate, the reasons for non-participation will be reported.

Within each country, the target number of centers participating in the study will be determined based on the capacity of each participating center to access patients meeting the eligibility criteria, as assessed by the feasibility study. Target number of centers may be adjusted accordingly.

Investigator selection will be performed independently in each country based on the feasibility assessment and eligibility criteria listed below.

Investigators may be hematologists, onco-hematologists or any other specialists involved in the management of adult CAD patients. Their eligibility will be based on the following criteria:

- Physicians working in centers managing patients with CAD and having available the appropriate facilities or equipment to perform research.
- Personally managing CAD patients
- Assessing or managing the thromboembolic risk in their CAD patients, or being informed by colleagues when their CAD patients present with a thromboembolic risk
- Agreeing to comply with the study protocol and data collection procedures.

Formatted: Indent: Left: 0,4 cm, Tab stops: 1,04 cm, Left

Protocol template for disease observational studies				
			Research and Development	
QSD-003149	Disease observational study	with disease	Application Date (DD/MM/YYYY) : dd-Mmm-09/11/2020	EFFECTIVE

<DD-MM-YYYY HH:mm:ss> < 15-01-2021 21:03:21 > UTC

primary data collection  
Study Number: GER-CAD-19-11180

Version number: ~~V6~~V7.0

## 10 DATA COLLECTION

### 10.1 DATA COLLECTION SCHEDULE

Pseudo-anonymized epidemiologic, clinical, and biologic data from patient's medical charts will be extracted by site staff from the initial date of CAD diagnosis until the earliest of death, end of data availability (*i.e.* lost to follow-up) or end of data collection set on January 1st, 2020. Diagnosis must have occurred between January 1st, 2009 and January 1st, 2019. Duration of follow-up will depend on time of diagnosis; a priori, enrolled patients diagnosed earlier during this time period will have a longer follow-up period than those diagnosed later. There will be no minimum duration of follow-up. However, HCRU analysis will require having data from patient medical records available for a minimum of time following a TE to ensure all costs associated with each TE are covered. Per-patient-per-month (PPPM) HCRU will be calculated during the variable follow-up period of up to 12 months after the TE diagnosis.

There will be no prospective follow-up period. No examinations or procedures apart from those occurring as part of the patient's routine clinical care are required for this study.

The schedule of events is described in Table 2: Schedule of Recommended Study Assessments

Since this study is retrospective in nature, results will be collected as available.

Table 2: Schedule of Recommended Study Assessments

Data to be collected	Assessments	Screening	Baseline	Follow-up
Eligibility criteria		X		
Written informed consent (IC)		X		
Demographics			X	
Medical History	Comorbidities; TE risk factors		X	X
CAD diagnosis history and disease status	Clinical findings; indicators of anemia and hemolysis		X	X

Property of the Sanofi-Aventis Groupe - strictly confidential

Protocol template for disease observational studies					
				Research and Development	
QSD-003149	Disease observational study	with disease	Application Date (DD/MM/YYYY) : dd-Mmm-09/11/2020	EFFECTIVE	

<DD-MM-YYYY HH:mm:ss> < 15-01-2021 21:03:21 > UTC

Formatted: Left, Tab stops: 8,89 cm, Centered + 17,1 cm, Right

primary data collection  
Study Number: GER-CAD-19-11180

Version number: ~~V6~~V7.0

Significant medical events	TE dates and types; previous history of TE		X	X
Relevant treatment history	CAD-specific treatment patterns; response to treatment		X	X
Direct HCRU related to TE	Hospitalizations and length of stay; outpatient, ER and ICU visits			X
Patient vital status	Cause of death; date of death			X

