MAIN DATA COLLECTED	
 
• Demographics: Date of birth (month, year); Sex
 
• Relevant medical history: Any chronic or serious disease other than CAD and diagnostic date; Risk factors for TE; Previous medical history of TE
 
• CAD characteristics: Age at onset of anemia or clinical symptoms; Age at diagnosis; Clinical presentation at or before diagnosis; Biological features at diagnosis; Transfusion history; Disease status over follow-up; History of hemolytic exacerbation/flares
 
• Thromboembolic events: Type of TE events (arterial, venous) and other events such as post-thrombotic syndrome and pulmonary hypertension, and dates
 
• Drug therapy associated with CAD: Agent/s (including any Corticosteroid Containing Therapy and Rituximab); Daily dose for corticosteroids; Duration of therapy, line of treatment; Treatment response (complete response, partial response, non-response); Splenectomy; Thromboprophylaxis
 

Property of the Sanofi-Aventis Groupe - strictly confidential

Protocol template for disease observational studies				
			Research and Development	
QSD-003149	Disease observational study protocol v. 6.0yyyy	with disease	Application Date (DD/MM/YYYY) :dd-Mmm- 09/11/2020	EFFECTIVE

<DD-MM-YYYY HH:mm:ss> < 15-01-2021 21:03:21 > UTC

Formatted: Left, Tab stops: 8,89 cm, Centered + 17,1 cm, Right

primary data collection  
Study Number: GER-CAD-19-11180

Version number: ~~V6~~V7.0

	
 
Direct HCRU associated with TE: All-cause inpatient admissions and length of stay (LOS); Outpatient visits; Admissions to ICU and LOS; Emergency room (ER) visits; Surgical and other major procedures
 
Patient vital status: Date of death; Cause of death
 

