#### CAD and risk of thromboembolic events (TEs)

Recent data suggest a correlation between CAD and thromboembolic events (TEs), which can impact quality of life and also lead to premature mortality (14, 15). TEs can also substantially increase disease burden and cost of treatment in CAD; in the general population, ten to thirty percent of patients die within 1 month of diagnosis of a venous thrombotic event (VTE), and among those who survive, 50% have long-term complications (16). An incident VTE has been estimated to cost between \$12 000 and \$15 000 in 2014 in the USA, which increased to \$18 000-\$23 000 when including subsequent complications (17).

Nevertheless, TE data in CAD is sparse, and the rarity of CAD limits the ability to perform large population-based studies. Several methodological limitations should be considered when interpreting existing TE data from the largest population-based studies in CAD and TE; a retrospective study in the USA involving a cohort of 608 individuals diagnosed with CAD from an insurance-based registry and nearly 6,000 matched controls recorded (venous and arterial) TE

Property of the Sanofi-Aventis Groupe - strictly confidential

Protocol template for disease observational studies					
				Research and Development	
QSD-003149	Disease observational study	with disease	Application Date (DD/MM/YYYY) : dd-Mmm- 09/11/2020	EFFECTIVE	

<DD-MM-YYYY HH:mm:ss> < 15-01-2021 21:03:21 > UTC

Formatted: Left, Tab stops: 8,89 cm, Centered + 17,1 cm, Right

primary data collection  
Study Number: GER-CAD-19-11180

Version number: ~~V6~~V7.0

during a 10-year period in 30 percent of those with CAD versus 18 percent of controls (adjusted hazard ratio [HR], 1.94; 95% confidence interval [CI], 1.64-2.30) (18), but misclassification due to coding errors inherent to claims data is likely. A smaller study from a Danish registry found an increased rate of TE in CAD patients as compared with age- and sex-matched controls (19), but there were also some methodology issues associated with the lack of validation of diagnostic codes in such registry.

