**Table 1 - Objectives and outcomes**

Objectives	Outcomes
Primary	

 
To estimate incidence rates of thrombotic events (TEs) in CAD
 
	
 
Crude incidence rate of TE (overall and by type)
 

Secondary	

 
To characterize TEs in CAD and the risk factors for developing TE in CAD
 
To estimate mortality rates in CAD, all-cause, and by underlying cause
 
To assess health care resource utilization (HCRU) associated with TEs in CAD
 
	
 
Analysis of thromboembolic complications in patients with CAD: 
 
Incidence rate of TE by type (arterial, venous) after CAD diagnosis
 
Cumulative incidence of TE after CAD diagnosis
 
Correlation between CAD-clinical severity and TE occurrence
 
 
 
OS (Overall Survival) in CAD / mortality rate: 
 
Mortality rate in CAD, all cause and cause-specific mortality
 
Overall survival
 
 
 
Direct HCRU associated with TE in CAD: 
 
Percentage of patients with TE-related inpatient hospitalizations, ER, ICU and outpatient visits
 
Length of stay of inpatient hospitalizations related to TEs
 
Number of procedures / surgeries associated with TE diagnosis and management
 
 
 

Property of the Sanofi-Aventis Groupe - strictly confidential

Protocol template for disease observational studies				
			Research and Development	
QSD-003149	Disease observational study protocol v. 6.0	with disease	Application Date (DD/MM/YYYY) : dd-Mmm- 09/11/2020	EFFECTIVE

<DD-MM-YYYY HH:mm:ss> < 15-01-2021 21:03:21 > UTC

Formatted: Left, Tab stops: 8,89 cm, Centered + 17,1 cm, Right

primary data collection  
Study Number: GER-CAD-19-11180

Version number: ~~V6~~V7.0

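### The minimum record time after a TE that the HCRU analysis requires has no exemption for death, so applied literally it selects survivors of the event

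*Protocol*

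**What the plan says.** Section 10.1 sets the general rule for the cohort: "There will be no minimum duration of follow-up". It then makes an exception for one analysis: "HCRU analysis will require having data from patient medical records available for a minimum of time following a TE". The stated reason is "to ensure all costs associated with each TE are covered". The minimum has no stated length, and death is not mentioned in that sentence. Earlier in the same section, data are extracted "until the earliest of death, end of data availability" (loss to follow-up) or 1 January 2020.

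The next sentence gives the measure: "Per-patient-per-month (PPPM) HCRU will be calculated during the variable follow-up period of up to 12 months after the TE diagnosis". Section 13.4 gives the unequal length of follow-up as the reason for using PPPM.

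On what is counted, Table 1 in section 6 has as an outcome "Percentage of patients with TE-related inpatient hospitalizations, ER, ICU and outpatient visits", together with length of stay and procedures tied to TEs. The data list in the synopsis, under HCRU associated with TE, instead names "All-cause inpatient admissions and length of stay (LOS", and the flow chart in section 2.2 does the same.

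**The concern.** A patient who dies a few days after a TE has a chart that ends a few days after the TE. If the HCRU analysis admits only patients with some minimum of records after the event, that patient fails the condition. Inclusion then depends on surviving the event whose burden is being measured. The patients lost may have a quite different pattern of emergency, inpatient and intensive care use from those who remain. HCRU associated with TEs is a secondary objective, and section 5.2 says the results will inform HTA submissions, so a survivors-only figure would be carried into those dossiers.

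The second question is what the figure means. If admissions are collected whatever their cause but reported as TE-related, something has to separate the two, and the variable list names no such item for admissions and visits.

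**Working it through.** **Inputs from the protocol.** N = 170 and a TE proportion of 20-30% (section 13.1). Section 5.1 states that in the general population "ten to thirty percent of patients die within 1 month of diagnosis of a venous thrombotic event". This is used below as an assumption for CAD and for all TE types. The protocol gives no figure for the HCRU set.

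**Reproducing the plan's own figure.** The half-width is 1.96 × √(p(1−p)/170). At p = 0.20 it is 6.01%, and at p = 0.30 it is 6.89%. These match the stated 6.0 and 6.9%, so 20-30% is a proportion of the 170 patients and can be turned into counts.

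**Patients with a TE.** 170 × 0.20 = 34; 170 × 0.30 = 51.

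**Deaths within one month of the TE.**
- 34 × 0.10 = 3.4 and 34 × 0.30 = 10.2, leaving 30.6 and 23.8.
- 51 × 0.10 = 5.1 and 51 × 0.30 = 15.3, leaving 45.9 and 35.7.

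A minimum of one month or more that does not exempt death could therefore remove about 3 to 15 patients, or 10-30% of the TE group.

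**Direction of the effect.** All resource-use values here are assumptions. Survivors have 10 inpatient days over 12 months, 10% use the ICU and 70% are hospitalised. Early deaths (share d = 10% or 30%) have L days over t months. Mean days per patient stand in for length of stay.
- Survivors only: 10/12 = 0.83 days PPPM.
- All patients, pooled: ((1−d) × 10 + d × L) / ((1−d) × 12 + d × t).
- All patients, mean of individual values: (1−d) × 10/12 + d × L/t.
- Mean days, ICU % and hospitalised %: averages of the two groups with weights 1−d and d.

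| Early deaths (assumed) | Pooled PPPM, d = 10% / 30% | Mean of individual PPPM | Mean days | ICU % | Hospitalised % |
|---|---|---|---|---|---|
| Excluded | 0.83 | 0.83 | 10.0 | 10 | 70 |
| L = 10, t = 0.5; ICU 60%, hospitalised 95% | 0.92 / 1.17 | 2.75 / 6.58 | 10.0 / 10.0 | 15 / 25 | 72.5 / 77.5 |
| L = 5, t = 0.5; ICU 30%, hospitalised 70% | 0.88 / 0.99 | 1.75 / 3.58 | 9.5 / 8.5 | 12 / 16 | 70 / 70 |
| L = 2, t = 0.1; ICU 10%, hospitalised 40% | 0.85 / 0.90 | 2.75 / 6.58 | 9.2 / 7.6 | 10 / 10 | 67 / 61 |

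Example, second scenario at d = 30%: (7 + 1.5)/(8.4 + 0.15) = 8.5/8.55 = 0.99.

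Exclusion lowers PPPM whenever early deaths use more per month than survivors (L/t above 10/12), which holds in all three scenarios. Mean days are the same or higher with exclusion, because patients who die early have less time to accumulate them. ICU use is the same or lower. The percentage hospitalised depends on whether early deaths reach hospital. The table also shows that a mean of individual PPPM values is driven by the shortest follow-up, whereas the pooled ratio is not.

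**Relatedness.** Set side by side, the synopsis and flow chart collect admissions of any cause, while Table 1 reports admissions related to TE. Section 10.3.1, item 6, lists dates for admissions and visits and length of stay for admissions, with no item that marks them as TE-related. Item 6.5 limits procedures to those related to CAD or TEs, which is still wider than TE alone.

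**The case against.** The strongest reply is that nothing says early deaths are dropped. The stated purpose is full cost capture, and a chart that ends in death already holds all the costs of that TE. The rule may be aimed at loss to follow-up and at TEs shortly before 1 January 2020. Section 7.1 reviews charts whether or not the patient is alive, and section 13.4 says records are not excluded for missing data. The length of the minimum can be left to the SAP, which is not shown. Much of this stands: a reader might infer that the protocol removes early deaths, but it does not say so, and the undefined length alone is no finding. What remains is that the protocol itself fixes an inclusion condition that a death can fail, and gives no exemption.

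It might also be inferred that PPPM makes any minimum unnecessary. That goes too far. PPPM corrects for length of follow-up only if use is roughly constant over time, and use after a TE is likely to be front-loaded. If 10 inpatient days all fall in month 1, PPPM is 10 for a patient lost at one month and 10/12 = 0.83 for one followed for 12. A minimum for censored patients therefore has a legitimate purpose.

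On relatedness, the reply is that item 6 sits under a heading about HCRU associated with TE, that Table 2 in section 10.1 also speaks of TE-related HCRU, and that the variable list is expressly non-exhaustive. A relatedness field may therefore exist in the eCRF. The mismatch in wording remains.

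**Conclusion.** The point holds as a gap in a stated inclusion rule. Applied as written, the condition in section 10.1 selects survivors of the TE. The possible loss of about 3 to 15 of 34 to 51 patients rests on three assumptions: a minimum of at least one month, deaths not counted as complete, and a one-month mortality taken from venous events in the general population rather than from CAD or arterial events.

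A reader might conclude that resource use would be understated throughout. The calculations do not support that. PPPM would probably be too low and ICU use equal or lower, but length of stay could be overstated and the percentage hospitalised could err in either direction. Nor do the documents show that all-cause use will be reported as TE-related. They show only that the collected item and the reported outcome are described differently. Both points concern a descriptive secondary objective and leave the primary incidence rate untouched. They are worth correcting because the TE group is small and the remedy is cheap.

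**What to change.** - In sections 10.1 and 13.4, state that follow-up ending in death counts as complete observation and is never a reason for exclusion from the HCRU analysis.
- Apply any minimum only to patients censored by loss to follow-up or by the 1 January 2020 cut-off.
- Define PPPM as total resource units divided by total patient-months, so that very short follow-up does not dominate.
- Reconcile the all-cause admissions in the synopsis and flow chart with the TE-related outcomes in Table 1. Either record TE-related yes/no for each admission or visit, or relabel the outcome as all-cause HCRU after TE.

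The cost is a few sentences and at most one extra eCRF field per admission or visit. The downside is that some patients with short follow-up enter the estimates; the pooled ratio limits their weight.

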## 10.2 DEFINITION OF SOURCE DATA

The primary data source for the study will be the patient medical record. All data will be captured in an electronic case report form (eCRF) and entered into an EDC system by the trained local site staff. No visits, examinations, or procedures apart from those occurring as part of the patient's routine clinical care are mandated as part of this study.

## 10.3 DATA COLLECTED

### 10.3.1 Participant data

Variables including but not limited to the following will be collected if available:

1. Demographics:
  - 1.1. Date of birth (month, year); Sex
2. Relevant medical history
  - 2.1. Any chronic or serious disease other than CAD and diagnostic date (e.g. AIHA; autoimmune disorders other than AIHA; known thrombophilia).
  - 2.2. Comorbidities: known thrombophilia; cardio-vascular conditions (CVCs): diabetes, hypertension, and hyperlipidemia; organ failure; cured or inactive malignant diseases; respiratory or cardiac deficiency; renal disease; hepatitis; inflammatory rheumatic disease ; obesity).

Protocol template for disease observational studies				
			Research and Development	
QSD-003149	Disease observational study protocol v. 6.0	with disease yyyy	Application Date (DD/MM/YYYY) :dd-Mmm- 09/11/2020	EFFECTIVE

<DD-MM-YYYY HH:mm:ss> < 15-01-2021 21:03:21 > UTC

primary data collection  
Study Number: GER-CAD-19-11180

Version number: ~~V6~~V7.0

3. CAD characteristics
  - 3.1. Age at onset of anemia
  - 3.2. Age at CAD diagnosis
  - 3.3. Clinical presentation at or before diagnosis (*e.g.* circulatory symptoms: acrocyanosis; anemia; fatigue; jaundice; shortness of breath; asthenia; dyspnea; hemoglobinuria; angina)
  - 3.4. Biological features at diagnosis (*e.g.* haemolytic screen at diagnosis (hemoglobin level (g/L), Lactate dehydrogenase (LDH) level (UI/L), haptoglobin, bilirubin (µmol/L), reticulocyte (count); DAT pattern; cold agglutinin titer at 4°C; thermal amplitude)
  - 3.5. Disease status over follow-up (*e.g.* history of hemolytic exacerbation/flare; markers of disease activity/indicators of hemolysis: (*e.g.* hemoglobin level (g/L), lactate dehydrogenase (LDH) level (UI/L), haptoglobin, bilirubin (µmol/L), reticulocyte count)
  - 3.6. Transfusion history (*e.g.* number of RBC units transfused and dates)
4. Thromboembolic events
  - 4.1. Type of TE events (arterial, venous) and other events such as post-thrombotic syndrome and pulmonary hypertension, and dates
  - 4.2. Conditions in the weeks prior to a TE (*e.g.* chemotherapy, immobilization; thromboprophylaxis; TE-related hospitalization, major surgery; trauma; fracture; oestrogen and progestrogene use; pregnancy/puerperium)
5. CAD history treatment
  - 5.1. Drug therapy (*e.g.* agent/s, daily dose for corticosteroids, duration of therapy), line of treatment and treatment response (complete response, partial response, non-response)
    - 5.1.1. Any Corticosteroid Containing Therapy (betamethasone, budesonide, dexamethasone, steroid, prednisone, prednisolone, methylprednisolone); Any Rituximab Containing Therapy; Bortezomib; Bendamustine, Eculizumab;
  - 5.2. Splenectomy
  - 5.3. Thromboprophylaxis

Property of the Sanofi-Aventis Groupe - strictly confidential

Protocol template for disease observational studies				
			Research and Development	
QSD-003149	Disease observational study protocol v. 6.0	with disease	Application Date (DD/MM/YYYY) : dd-Mmm- 09/11/2020	EFFECTIVE

<DD-MM-YYYY HH:mm:ss> < 15-01-2021 21:03:21 > UTC

Formatted: Left, Tab stops: 8,89 cm, Centered + 17,1 cm, Right

primary data collection  
Study Number: GER-CAD-19-11180

Version number: ~~V6~~V7.0

6. Direct HCRU associated with TE
  - 6.1. Inpatient admission dates and hospitalization length of stay (LOS)
  - 6.2. Outpatient visit dates
  - 6.3. ICU admission dates and LOS
  - 6.4. Emergency room (ER) visit dates
  - 6.5. Surgical and other major procedures related to CAD/TEs
7. Patient vital status
  - 7.1. Cause of death
  - 7.2. Date of death

A complete description of variables will be detailed in the Statistical Analysis Plan (SAP). All study data will be recorded according to the schedule of recommended assessments as outlined in Table 2. However, completion of a particular assessment will be at the discretion of the participating investigator and dependent on local standards of care and individual physician practice patterns. It is anticipated that death may not be always recorded in real-world practice, which may result in an under-estimation of mortality rates in the CAD population.

